6.5 POOLING OF CENTRES

Not applicable as this is a single centre trial.

6.6 HANDLING OF MISSING DATA AND OUTLIERS

For evaluation of primary and secondary endpoints a measurement obtained at baseline and on-treatment per period is required. If a patient misses a visit, the missing data will not be imputed. The random intercept model will handle missing data based on a likelihood method under the "missing at random" assumptions.

Generally, it is not planned to impute missing values for further safety with the exception of missing or incomplete AE dates. These will be handled according to BI standards (see SOP 001-MCG-156_RD-01 ([3](#)) for missing AE dates

6.7 BASELINE, TIME WINDOWS AND CALCULATED VISITS

Baseline is defined as the last measurement before first study drug administration in each treatment period.

For endpoints related to methacholine challenge baseline refers to the measurement obtained from the baseline bolus MCh challenge prior to administration of trial medication within each treatment period. The post-diluent value refers to the last measurement before methacholine administration (i.e. timepoint -0:05 relative to methacholine challenge).

Measurements taken after start of administration of trial medication will be considered on-treatment values or follow-up values, based on the definition of the study analysis phases in Section [6.1](#).

Adherence to time windows will be checked at the BRPM/DBLM.

7. PLANNED ANALYSIS

The format of the listings and tables will follow the BI guideline "Reporting of clinical trials and project summaries" ([9](#)).

The individual values of all subjects will be listed, sorted by treatment sequence, subject number and visit (if visit is applicable in the respective listing). AE listings will be sorted by assigned treatment (see Section [7.8.1](#) below for details). The listings will be contained in Appendix 16.2 (SDL) of the CTR.

The following standard descriptive statistical parameters will be displayed in summary tables of continuous variables:

N	number of non-missing observations
Mean	arithmetic mean
SD	standard deviation
Min	minimum
Median	median
Max	maximum

For endpoints related to MCh challenge, the set of summary statistics is: N / Mean / SD / Min / Q1 (1st quartile) / Median / Q3 (3rd quartile) / Max.

Tabulations of frequencies for categorical data will include all possible categories and will display the number of observations in a category as well as the percentage (%) relative to the respective treatment group. Percentages will be rounded to one decimal place. The category missing will be displayed only if there are actually missing values. Percentages will be based on all subjects in the respective analysis set whether they have non-missing values or not.

7.1 DEMOGRAPHIC AND OTHER BASELINE CHARACTERISTICS

Only descriptive statistics are planned for this section of the report.

7.2 CONCOMITANT DISEASES AND MEDICATION

Concomitant diseases will be coded according to the most recent version of the Medical Dictionary for Regulatory Activities (MedDRA). Concomitant medication will be coded according to the most recent version of the World Health Organisation – Drug Dictionary (WHO-DD).

Only descriptive statistics are planned for this section of the CTR.

A medication will be considered concomitant to a treatment, if

- it is ongoing at the time of first administration of the respective treatment or
- it starts within the on-treatment phase of the respective treatment (see Section [6.1](#)).

7.3 TREATMENT COMPLIANCE

Treatment compliance will not be analysed as a specific endpoint. Any deviations from complete intake will be addressed in the BRPM/DBLM (cf. Section [6.2](#)) and described in the CTR.

7.4 PRIMARY ENDPOINT

CTP: *The primary endpoint absolute change from baseline in maximum reduction in FEV1 (refer to Section 5.1.1 of the CTP) is defined as the difference between the maximum reduction in FEV1 obtained during the treatment challenge and during the baseline challenge.*

The primary endpoint will be analyzed based on the MCS.

Descriptive statistics and boxplots of the primary endpoint by treatment (and by trial part) will be provided.

As main analysis, the following model will be applied to the main part of the trial (part II).

Statistical model

CTP: [...] this primary endpoint will be analysed using a mixed effects model based on the MCS:

$$y_{imj} = \mu + \pi_m + \tau_j + \gamma b_{im} + \gamma' b_i' + s_i + e_{imj},$$

where $i = \text{subject } 1, \dots, N$, $m = \text{period } 1, \dots, 4$, $j = \text{treatment } 1, \dots, 4$

y_{imj}	CfB in maximum FEV₁ reduction for the i^{th} subject and the m^{th} period, receiving randomised treatment j
μ	overall intercept,
π_m	m^{th} period effect,
τ_j	j^{th} treatment effect,
b_{im}	baseline value for subject i in period m (period baseline),
γ	associated covariate effect of period baseline,
b'_i	the subject baseline value (mean of period baselines) for subject i,
γ'	associated covariate effect of subject baseline,
s_i	the random effect of subject i,
e_{imj}	the random error associated with subject i who received treatment j in period m.

The treatment comparisons will be the contrast (difference) between active dose and placebo at the endpoint visit. Adjusted means (Least Squares Means) as well as 2-sided 90% CIs will be provided.

For the random ‘subject’ effect in the above model a Variance Components (VC) covariance structure will be used; in case of convergence problems refer to Additional Section [9.1](#). The SAS procedure MIXED will be used involving the restricted maximum likelihood estimation and the Kenward-Roger approximation for denominator degrees of freedom. This approach is described in Kenward and Roger ([11](#)).

Programming details are provided in Section [9.2.1](#).

7.5 SECONDARY ENDPOINTS

The secondary endpoints will be analyzed based on the MCS.

Relative change from baseline in FEV₁ AUC_{0-tz} following bolus MCh challenge:

CTP: *The secondary endpoint relative change from baseline in FEV₁ AUC_{0-tz} (see Section 5.1.2 of the CTP) is defined as the ratio of FEV₁ AUC_{0-tz} obtained during the treatment challenge and during the baseline challenge. During each challenge, the area above the curve of the absolute change in FEV₁ from post-diluent value will be calculated from time 0*

to t_z using the trapezoidal rule (refer to 001-MCG-163). The time t_z refers to the last time point before recovery of FEV_1 to within 95% of post-diluent value.

Note that in case a subject's FEV_1 does not recover to within 95% of post-diluent value the time t_z refers to the last timepoint at which FEV_1 was measured for that subject in that period. Furthermore, if a subjects FEV_1 does not decrease below 95% of post-diluent value the AUC will not be defined and hence not be calculated.

Descriptive statistics and boxplots of the secondary endpoint by treatment (and by trial part) will be provided.

As main analysis, the following model will be applied to the main part of the trial (part II). The statistical model used for this secondary endpoints is comparable to the one specified for the primary endpoint, despite the fact that it is evaluated on the logarithmic scale.

Statistical model

CTP: [...] this secondary endpoint will be analysed using a mixed effects model on the logarithmic scale based on the MCS:

$$y_{imj} = \mu + \pi_m + \tau_j + \gamma b_{im} + \gamma' b'_i + s_i + e_{imj},$$

where $i = \text{subject } 1, \dots, N$, $m = \text{period } 1, \dots, 4$, $j = \text{treatment } 1, \dots, 4$

y_{imj}	Logarithm of CFB in FEV_1 AUC_{0-t_z} consideration for the i^{th} subject and the m^{th} period, receiving randomised treatment j
μ	overall intercept,
π_m	m^{th} period effect,
τ_j	j^{th} treatment effect,
b_{im}	Logarithm of baseline value for subject i in period m (period baseline),
γ	associated covariate effect of period baseline,
b'_i	Logarithm of the subject baseline value (mean of period baselines) for subject i ,
γ'	associated covariate effect of subject baseline,
s_i	the random effect of subject i ,
e_{imj}	the random error associated with subject i who received treatment j in period m .

To this end, the endpoint will be log-transformed (natural logarithm) prior to fitting the model given above. The difference between the expected means for $\log(\text{Active}) - \log(\text{Placebo})$ will be estimated by the difference in the corresponding adjusted means (Least Squares Means), and a two-sided 90% confidence interval based on the t-distribution will be computed. These quantities will then be back-transformed to the original scale to provide the point estimate and 90% CIs for each endpoint.

For the random ‘subject’ effect in the above model a Variance Components (VC) covariance structure will be used; in case of convergence problems refer to Additional Section [9.1](#).

The SAS procedure MIXED will be used involving the restricted maximum likelihood estimation and the Kenward-Roger approximation for denominator degrees of freedom. This approach is described in Kenward and Roger ([11](#)).

Programming details are provided in Section [9.2.1](#).

Time to recovery of FEV₁ to within 95% of post-diluent value

CTP: *The secondary endpoint time to recovery of FEV₁ within 95% of post-diluent value (see Section 5.1.2 of the CTP) is defined as the time from maximum reduction to last time before recovery to within 95% of pre-MCh challenge during each challenge. The time obtained from the treatment challenge represents the endpoint, while the time obtained from the baseline challenge will be used for the baseline correction in the analysis.*

Descriptive statistics of the secondary endpoint by treatment (and by trial part) will be provided.

Kaplan-Meier (KM) curves will be plotted for the recovery of FEV₁ within 95% of post-diluent value by treatment irrespective of the period it is administered in, for both trial parts separately as well as combined, if applicable.

As a main analysis the following model will be applied to the main part of the trial (part II).

Statistical model

CTP: [...] this endpoint will be analysed using a Cox proportional hazards model as given below based on the MCS. The model includes the treatment effect and an effect for subject baseline. Thereby, the subject baseline is calculated as median of all period baselines per subject. Breslow’s method for handling ties will be used.

The hazard function for the i^{th} subject is assumed to be

$$\lambda_i(t) = \lambda_0(t) \cdot \exp\{\beta_1 X_{1i} + \beta_2 X_{2i} + \beta_3 X_{3i}\},$$

where $i = 1, \dots, N$,

$\lambda_0(t)$ is the unspecified, non-negative, baseline hazard function

- $\beta_{1,2,3}$ are the unknown regression coefficients
- X_{1i} represents the treatment group
- X_{2i} represents the subject baseline (median of period baselines)
- X_{3i} represents the period

For treatment comparisons the hazard ratios of BI 443651 vs. Placebo and asymptotic 95% Wald confidence intervals will be estimated. A hazard ratio of greater than one means that BI 443651 is not inferior to placebo.

Programming details are provided in Section [9.2.1](#).

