7.3.2 Secondary endpoint analyses

The secondary endpoint relative change from baseline in $\text{FEV}_1 \text{ AUC}_{0-\text{tz}}$ (see [Section 5.1.2](#)) is defined as the ratio of $\text{FEV}_1 \text{ AUC}_{0-\text{tz}}$ obtained during the treatment challenge and during the baseline challenge. During each challenge, the area above the curve of the absolute change in FEV_1 from post-diluent value will be calculated from time 0 to tz using the trapezoidal rule (refer to [001-MCG-163](#)). The time tz refers to the last time point before recovery of FEV_1 to within 95% of post-diluent value.

This secondary endpoint will be investigated using descriptive statistics for both trial parts separately and combined.

For the main part of the trial (part II), this secondary endpoint will be analysed using a mixed effects model on the logarithmic scale based on the MCS:

$$y_{imj} = \mu + \pi_m + \tau_j + \gamma b_{im} + \gamma' b'_i + s_i + e_{imj},$$

where i = subject 1,..., N, m = period 1,...,4, j = treatment 1,...,4

y_{imj}	Logarithm of CfB in $\text{FEV}_1 \text{ AUC}_{0-\text{tz}}$ consideration for the i^{th} subject and the m^{th} period, receiving randomised treatment j
μ	overall intercept,
π_m	m^{th} period effect,
τ_j	j^{th} treatment effect,
b_{im}	Logarithm of baseline value for subject i in period m (period baseline),
γ	associated covariate effect of period baseline,
b'_i	Logarithm of the subject baseline value (mean of period baselines) for subject i ,
γ'	associated covariate effect of subject baseline,

Proprietary confidential information © 2017 Boehringer Ingelheim International GmbH or one or more of its affiliated companies

s_i the random effect of subject i,
 e_{imj} the random error associated with subject i who received treatment j
in period m.

To this end, the endpoint will be log-transformed (natural logarithm) prior to fitting the model given above. The difference between the expected means for log(Active)-log(Placebo) will be estimated by the difference in the corresponding adjusted means (Least Squares Means), and a two-sided 90% confidence interval based on the t-distribution will be computed. These quantities will then be back-transformed to the original scale to provide the point estimate and 90% Cis for each endpoint.

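### SAP 7.5 drops challenges in which FEV1 never falls below 95% of post-diluent from the AUC ratio; if the drug augments bronchoconstriction, this pulls the ratio toward 1

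*SAP*

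**What the plan says.** Protocol 7.3.2 and SAP 7.5 define the endpoint as the AUC0-tz of the treatment challenge divided by that of the baseline challenge in the same period. The area is measured down from the post-diluent FEV1, and tz is the last time before FEV1 is back within 95% of that value. On the analysis scale, SAP 7.5 states that "the endpoint will be log-transformed (natural logarithm) prior to fitting the model given above".

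SAP 7.5 adds a note with two rules. If FEV1 does not recover, tz becomes the last measured time, so the challenge stays in. If FEV1 never drops under 95% of the post-diluent value, "the AUC will not be defined and hence not be calculated", so the challenge has no value.

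SAP 6.6 requires both members of the pair: "For evaluation of primary and secondary endpoints a measurement obtained at baseline and on-treatment per period is required". Its next sentence, "If a patient misses a visit, the missing data will not be imputed", concerns missed visits and gives no rule for an undefined AUC. It then says that "The random intercept model will handle missing data based on a likelihood method under the" missing-at-random assumption.

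In the public text there is no substitute value, no sensitivity analysis and no planned count of undefined AUCs. SAP 7.6 (further endpoints) is not in the public text, so it cannot be checked for a related analysis.

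**The concern.** A challenge with a fall under 5% is not missing. It is a fully observed, very mild response, and the rule turns it into a missing value because of its size. At the other end of recovery, the same note keeps the challenge. The rule therefore trims the mild end of the distribution of this endpoint. (Rescue medication is handled separately, through the methacholine set, and is not considered here.)

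The trial exists to see whether acetylcholinesterase inhibition augments bronchoconstriction (Protocol 2.1 and 2.3). If it does, falls under 5% on Day 2 will be more common on placebo than on active drug. Removing them raises the placebo mean of the log ratio more than the active mean, so the estimated harm shrinks. A likelihood-based mixed model corrects for missingness explained by observed data; it does not correct for missingness determined by the unrecorded value itself.

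**Working it through.** **The plan's own figure.** The documents give no precision or event frequency for the AUC endpoint. The only related figure is for the primary endpoint (Protocol 7.7): precision 0.112 L at N = 32 and SD 0.24 L. It reproduces with df = 3 x 32 - 6 = 90:

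t(0.95, 90) x SD x sqrt(2/N) x sqrt(chi2(0.95, 90)/90) = 1.662 x 0.24 x 0.25 x sqrt(113.15/90) = 0.0997 x 1.121 = 0.112 L.

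The rule does not affect this figure. Its SDs are used below only to set a scale.

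**Step 1: which losses can bias.** A period is lost if either challenge is undefined.
- The baseline challenge precedes dosing in that period. Absent carry-over, its chance of being undefined does not depend on treatment, so the loss costs precision.
- The Day 2 challenge follows dosing. Its chance of being undefined depends on the response itself, so this loss can bias.

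In an illustrative scenario (assumed post-diluent FEV1 3.0 L, mean fall 0.60 L, between-subject SD 0.20 L, per-challenge SD 0.24/sqrt(2) = 0.17 L, extra fall on active 0.2 L), 7.5% of placebo and 4.8% of active periods are lost. About 4.3 of the 7.5 points come from the baseline challenge. The difference between arms is 7.5% - 4.8% = 2.7 points, or 0.027 x 32 = 0.9 of a period.

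**Step 2: how often a fall could stay under 5%.** This is not in the documents. With a normally distributed fall, P = Phi((5 - mean)/SD). The assumed SDs are 5.7% (0.17/3.0), 8% (0.24/3.0) and 10% (0.30/3.0).

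| Mean fall | P(fall < 5%), SD 5.7% to 10% |
|---|---|
| 30% | 0.0% to 0.6% |
| 25% | 0.0% to 2.3% |
| 20% | 0.4% to 6.7% |
| 15% | 4.0% to 15.9% |

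Inclusion criterion 5 requires a methacholine dose that produced at least a 20% fall, and the bolus equals the cumulative screening dose (Flow Chart note 9). The upper rows are therefore the more plausible ones.

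**Step 3: effect on the ratio.** Treat log AUC on Day 2 as normal with SD s, true ratio R, and a share p of placebo challenges below the cut. This treats the 5% cut as a cut on log AUC and ignores the covariates. Put z0 = Phi^-1(p), zA = z0 - ln(R)/s and lambda(z) = phi(z)/(1 - Phi(z)). Then

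estimated ratio = exp{ ln R + s x [lambda(zA) - lambda(z0)] }.

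Example with R = 1.50, s = 0.5, p = 5%: z0 = -1.645 and zA = -1.645 - 0.811 = -2.456. lambda(z0) = 0.1086 and lambda(zA) = 0.0197. The exponent is 0.4055 + 0.5 x (0.0197 - 0.1086) = 0.361, so the estimate is 1.435.

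| Placebo below cut | Active below cut | Estimated ratio, true 1.50 (s = 0.8 to 0.5) |
|---|---|---|
| 1% | 0.1% to 0.2% | 1.477 to 1.482 |
| 2% | 0.2% to 0.5% | 1.459 to 1.468 |
| 5% | 0.7% to 1.6% | 1.420 to 1.435 |
| 10% | 1.8% to 3.7% | 1.372 to 1.392 |

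A true ratio of 1.0 stays 1.0. A true ratio of 1.25 becomes about 1.24 at 1% and 1.18 to 1.19 at 10%.

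**Step 4: cross-check.** Simulating the four-sequence crossover with the SAP model gave the same direction whenever the drug added a fixed amount to the fall. When the drug multiplied the response, the shift was small, and at a ratio of 1.3 mostly within simulation noise. On a 0-3 h area expressed as a difference in L.h, the shift from dropping these periods was about 1% to 6%.

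**The case against.** The strongest reply is that the rule follows from the protocol. If FEV1 never leaves the 95% zone there is no tz, and a zero area has no logarithm; the SAP only makes this explicit. That is right: some rule was needed, and this is not a conflict between protocol and SAP. It does not make the discarded challenges ignorable.

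Second, the effect is limited. The primary endpoint, maximum FEV1 reduction, needs no 5% fall, so mild responses stay in the main safety comparison. Protocol 7.2 describes the trial as exploratory, with intervals read as estimates. The difference expected in Protocol 7.7 is 0.06 L, well under the 0.2 L regarded as relevant, and a smaller effect brings a smaller bias. All of this stands.

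Third, losses will be partly visible. SAP 7 tabulates the number of non-missing observations, and SAP 7.5 gives descriptive statistics by treatment. These counts will not show whether the undefined AUC was at baseline or on Day 2, and only the latter matters for bias.

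A reader might infer a larger bias by giving undefined areas a small floor value and comparing. The documents supply no floor, and on the log scale the answer depends on the choice. At an assumed mean fall of 0.60 L and an extra fall of 0.2 L, floors from 0.05 down to 0.001 L.h gave ratios from 1.65 to 1.91, against 1.58 with the periods dropped. No single figure from that exercise measures the bias.

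**Conclusion.** The concern holds for this one secondary endpoint, conditionally. The rule selects on the outcome at the Day 2 challenge, and missing at random does not cover that. If the drug worsens the response, the ratio is pulled toward 1, the unsafe direction in a trial looking for harm.

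A reader might infer that the rule always favours the drug, or that every lost period adds bias. Neither is supported. With no effect there is no bias; with a protective effect, protection would be understated (a true 0.80 becomes 0.82 at 1% and 0.87 at 10%, with s = 0.5). Losses from a mild baseline challenge do not differ by treatment.

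On the Step 3 assumptions, a true ratio of 1.50 loses about 1% to 3% of its value if 1% to 2% of placebo challenges are below the cut, and about 4% to 9% if 5% to 10% are. The frequency is unknown and probably low, so the likely effect is modest. This is worth correcting because the correction is cheap, not because the planned analysis is invalid.

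**What to change.** Keep the log-ratio AUC0-tz analysis as planned in the protocol, and add three items to SAP 7.5.

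1. A prespecified sensitivity analysis of the area between post-diluent and observed FEV1 over 0-3 h, calculated for every challenge, including those with little or no fall. Analyse treatment minus baseline in L.h with the same mixed model (period and subject baselines taken from the 0-3 h area) and a two-sided 90% interval. Spirometry times are identical to 3 h at both challenges (Flow Chart notes 18 and 23; Protocol 6.2), and the original scale avoids the logarithm of zero.
2. A table of the number of undefined AUCs by treatment and by challenge (baseline or Day 2).
3. A statement that absence of augmentation will not be concluded from the AUC ratio if the two analyses disagree.

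If the unpublished SAP 7.6 already contains a fixed-window area, it need only be named here as the sensitivity analysis.

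The cost is one derived variable, one extra model and one table; no new data are needed. The 0-3 h window leaves out the Day 2 measurements at 3.5 to 8 h, so prolonged obstruction would not be captured. For that reason it should supplement the planned endpoint and not replace it.

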7.7 EXTENT OF EXPOSURE

Treatment exposure will be listed by means of the date and time of drug administration.

7.8 SAFETY ANALYSIS

All safety analyses of further safety parameters of interest will be performed on the treated set (and will be presented for both trial parts combined).

